1. OVERVIEW

Radiosurgery Dose Reduction for Brain Metastases on Immunotherapy (RADREMI): A Prospective Pilot Study

Principal Investigator: [name]

Co-Investigators: [name] PhD; [name]; [name], [name] [name] (Case Western Reserve University)

[figure not shown]
Primary objective: To demonstrate 6 month symptomatic radiation necrosis (SRN) rates following ICI concurrent with dose-reduced SRS

Secondary objectives: 6-month local control (LC), 6-month radiographic radiation necrosis rates, 12-month SRN, 12-month LC, Differences in SRS and LC at 12-months for SRS modality, single versus multi-agent ICI, and melanoma versus non-melanoma brain metastases

Eligibility

- ≥ 18 years old
- Biopsy-proven primary malignancy
- Metastatic brain disease as visualized on brain MRI
- No previous whole brain radiation therapy (WBRT)
- Expected survival of 6+ months using ds-GPA

Sample size: 42

2. BACKGROUND & RATIONALE

Epidemiology

Occurring ten times more frequently than primary brain tumors, brain metastases are by far the most common intracranial malignancy (Nabors et al., 2017). Associated with a median overall survival of 4-5 months, brain metastases afflict more than 200,000 people annually in the United States, comprising up to 30% of adults with cancer (Pruitt et al., 2017; Gibney et al., 2012; Fife et al., 2004; Davies et al., 2011).

Treatment of Brain Metastases

In general, treatment of metastatic brain disease involves surgical resection, whole brain radiation therapy (WBRT), stereotactic radiosurgery (SRS), and/or systemic therapy. While conventional systemic therapies alone are typically not sufficient to control intracranial disease due to the presence of the blood-brain barrier, newer studies suggest efficacy of immunotherapy – predominantly via immune checkpoint inhibitors (ICI). Recent Level I evidence in patients with metastatic melanoma indicates that the 6-month local control rate of brain metastases treated with multi-agent ICI alone (nivolumab + ipilimumab) is 57% (Tawbi et al., 2018), compared to the 24% rate of ipilimumab alone (Margolin et al., 2012), the 22% rate of pembrolizumab alone (Goldberg et al., 2016), or the 50% rate of ipilimumab + fotemustine (DiGiacomo et al., 2012). While the local control rate of multi-agent ICI is encouraging, it is important to remember that the 57% rate remains vastly inferior to the six-month local control rates of 87-91% achieved following single-fraction SRS administered via linear accelerator or Gamma Knife (Tawbi et al., 2018; Bernard et al., 2012; Minniti et al., 2017; Matsunaga et al., 2018). Candidates for SRS are typically patients with 1-10 brain metastases, while patients exceeding 10 brain metastases often receive WBRT instead of SRS (Yamamoto et al., 2014).

Morbidity of Standard-Dose Stereotactic Radiosurgery + Immunotherapy for Metastatic Brain Disease

A potential late toxicity of high-dose SRS for brain metastases is symptomatic radiation necrosis, which is associated with focal inflammation and intracranial edema at the irradiated site, often requiring steroid treatment (which is in itself counterproductive for optimizing efficacy of ICI; Kotecha et al., 2019) and/or craniotomy for resection of the necrosis in situations where the edema manifests as acute and potentially life-threatening neurologic deterioration. Albeit limited compared to the addition of SRS, the efficacy of multi-agent ICI alone in achieving local control of more than half of brain metastases (including a 26% complete response rate) at six months brings forth an important question: Are the doses of SRS currently being administered for brain metastases excessive given that a large proportion of the metastatic brain disease population is receiving systemic ICI treatment?

Prior to the widespread use of immunotherapy, the radiographic radiation necrosis rate of SRS for metastatic brain disease was less than 5% (with the symptomatic radiation necrosis rate less than 3%); however, a recent large study of 115 patients has indicated that in the current immunotherapy era, the true rate of symptomatic radiation necrosis with SRS + ICI is as high as 20% (Martin et al., 2018). Unfortunately, studies examining SRS + ICI have rarely reported radiation necrosis

rates, and the vast majority of those doing so have failed to report symptomatic radiation necrosis rates (Cohen-Inbar et al., 2017; Williams et al., 2017; Anderson et al., 2017; Yusuf et al., 2017; Chen et al., 2018). Only two studies have reported symptomatic radiation necrosis rates, revealing a range from 12-20% of treated patients (Skrepnik et al., 2017; Martin et al., 2018). Unlike the majority of studies examining SRS + ICI, these two studies allow for determination of symptomatic radiation necrosis rates per patient rather than per treated lesion; for disease where it is common for patients to require treatment for multiple lesions, rates determined per patient will be substantially higher than those determined per treated lesion.

This is not a trivial consideration, as up to 1 in 5 patients treated with SRS for metastatic brain disease may develop symptomatic radionecrosis. This toxicity has the potential to affect outcomes in this patient population, given the proven association between steroid use and poorer overall survival for patients on ICI (Kotecha et al., 2019), and the side effect profile of bevacizumab when used to address symptoms. The paucity of studies examining symptomatic radiation necrosis following SRS in brain metastasis patients who are receiving immunotherapy is further exacerbated by the lack of detail in the literature regarding radionecrosis rates relative to immunotherapy and SRS administration, and the dearth of prospectively collected data (Lehrer et al., 2019). To date, only one study has reported the time from SRS to radiographic radiation necrosis rate (median: 14.7 months), with no studies reporting the time from SRS to symptomatic radiation necrosis (Skrepnik et al., 2017).

Proposed Solution to Metastatic Brain Disease Treatment-Related Morbidity

A potential solution to this problem involves dose-reduced SRS to a level which substantially reduces radionecrosis risk without sacrificing the approximately 80-85% six-month local control provided by the present dosing schema, which from RTOG 90-05 has remained 24 Gy for lesions 0-2 cm, 18 Gy for lesions 2.1-3 cm, and 15 Gy for lesions 3-4 cm (Shaw et al., 2000). To maintain a dosing schema less toxic than the RTOG 90-05 regimen while remaining within SRS doses established by Level I evidence to provide local control (Brown et al., 2017), we propose the following dose-reduced SRS protocol for this *Radiosurgery Dose Reduction for Brain Metastases on Immunotherapy* (RADREMI) prospective pilot study: 18 Gy (0-2 cm lesions), 14 Gy (2.1-3 cm lesions), and 12 Gy (3-4 cm lesions) for brain metastases patients receiving at least one immunotherapy agent. These doses are consistent with Level I evidence comparing SRS with whole brain radiation therapy for metastatic brain disease, which revealed that SRS doses of 12-20 Gy were sufficient to provide local control (Brown et al., 2017). For perspective, it is important to remember that RTOG 90-05 was not a dose finding study, but rather a dose tolerance study; subsequent work has established improved local control compared to RTOG 90-05 while using lower doses than the RTOG 90-05 regimen (Shehata et al., 2004; Colaco et al., 2016). Given the efficacy of immunotherapy alone in treating melanoma brain metastases (Tawbi et al., 2018), it is reasonable to hypothesize that a lower SRS dose than the RTOG 90-05 schema will result in a combinatorial effect sufficient to provide local control without resulting in the 20% symptomatic necrosis rate seen with the present dosing schema (Martin et al., 2018).

Summary and Rationale

In summary, this study seeks to assess the efficacy and safety of radiosurgery dose reduction for brain metastases patients receiving immunotherapy. We hypothesize that: 1. Dose-reduced SRS will reduce the risk of radionecrosis compared to the 16% average rate per patient from the existing concurrent SRS + ICI literature (Skrepnik et al., 2017; Martin et al., 2018) with current SRS dose, and 2. Dose-reduced SRS demonstrates non-inferior efficacy (measured primarily through six-month local tumor control) compared to the 80% local control rate associated with the RTOG 90-05-established SRS dosing parameters. For the purposes of this study, radionecrosis will be defined as clinical symptomatology following SRS requiring steroid utilization and/or operative intervention in combination with imaging features strongly suggesting radionecrosis as demonstrated utilizing routine MRI, MR Perfusion, MR Spectroscopy, and/or PET imaging. Although the definition of concurrent SRS+ICI has varied greatly in the literature, ranging from 2 weeks to 4 months with some studies defining administration within 4 months as concurrent (Anderson et al., 2017; Chen et al., 2018); for the purposes of this study, concurrent therapy will be defined as ICI administered within 30 days of SRS. We also hope to explore SRS radionecrosis rates in multi-agent versus single-agent immunotherapy, as well as in melanoma versus non-melanoma brain metastases. Local control will be defined as a less than 20% increase in tumor size following SRS, as previously described using Response Assessment in Neuro-Oncology (RANO) criteria (Lin et al., 2015).

3. OBJECTIVE(S)

3.1 Primary Objective

To evaluate toxicity rates of brain metastasis after ICI concurrent with SRS at six months with regard to symptomatic radiation necrosis, defined as a 6-month rate of clinical symptomatology requiring steroid administration (i.e. Decadron), bevacizumab (Avastin), and/or operative intervention concomitant with advanced and routine brain imaging findings consistent with radiation necrosis.

3.2 Secondary Objectives

- 6-month local control
- 6-month radiographic radiation necrosis
- 12-month symptomatic radiation necrosis
- 12-month local control
- 12-month radiographic radiation necrosis
- 12-month local control rate by SRS modality
- 12-month local control rate by single versus multi-agent ICI
- 12-month local control rate by melanoma versus non-melanoma brain metastases
- 12-month symptomatic radiation necrosis rate by SRS modality
- 12-month symptomatic radiation necrosis rate by single versus multi-agent ICI
- 12-month symptomatic radiation necrosis rate by melanoma versus non-melanoma brain metastases

4. OUTCOME MEASURES

4.1 Primary Outcome Measure

6 month symptomatic radiation necrosis, defined as a 6-month rate of clinical symptomatology requiring steroid administration (i.e. Decadron) and/or operative intervention concomitant with advanced and routine brain imaging findings consistent with radiation necrosis. Follow-up MRIs will be fused with the planning scan for this assessment.

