8.6 Long Term Follow up

Subjects will be followed approximately every 3 months (+/- 30 days) after SRS for 1 year. A detailed medical history (including necessity of any steroid administration), toxicity assessment and physical examination including vital signs will be performed at each visit. Each follow-up over this time period will also include a Brain MRI with the following sequences: without contrast, with contrast, FLAIR, Diffusion Tensor Imaging (DTI) and Perfusion Weighted Imaging (PWI). The MRI will be analyzed per RANO BM criteria (Section 11) for assessment of local control. The MRI will also be analyzed for radiation necrosis as discussed in Section 12. Neurologic status will be assessed using the Neurologic Assessment in Neuro-Oncology (NANO) scale (Nayak et al., 2017).

After the 1-year (12-month) follow-up period, subjects will be followed according to their treating physician per standard of care every 3-6 months. MRI Brain obtained during this time period may be used for assessment of primary and secondary endpoints; however, are not mandated to be obtained at particular time intervals. Patients who are unable to travel to Indiana University for follow-up appointments will have records sent to Indiana University at each follow-up.

From year 2-5, the follow up period will be determined by their treating physician per standard of care, generally every 3-6 months. MRIs will be obtained per treating physician discretion.

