9. STUDY CALENDAR

	Baseline Screening*	SRS (stereotactic radiosurgery) *	1 Month Follow Up ^{1*}	3 Month Follow Up ^{1*}	6 Month Follow Up ^{1*}	9 Month Follow Up ^{1*}	12 Month Follow Up ^{2*}
	Within 30 days of SRS	Gamma Knife or Linear Accelerator (LINAC)	30 days post SRS	90 days post SRS	180 days post SRS	270 days post SRS	1 years post SRS
Radiation Oncology consult and consent	X						
Medical History (including steroid usage)	X		X	X	X	X	X
Physical Examination	X		X	X	X	X	X
Vitals: weight/ht. BP ⁷	X	X	X	X	X	X	X
ds-GPA ⁵	X						
Diagnostic MRI Brain ⁶	X						
KPS	X						
MRI Brain Planning Scan ⁴		X					
ALC	X						
Toxicity assessment			X	X	X	X	X ⁸
MRI Brain with and without contrast ³			X	X	X	X	X

Footnotes:

1. Variations of +/- 30 days from the scheduled visit are permitted
2. After 12-months post-SRS, subjects will be followed at physician's discretion, approximately every 3-6 months per standard of care. Any MRI Brain, physical exam or vitals obtained at these appointments will be gathered. However, if these procedures are not performed per standard of care, this will not be a deviation.
3. MRI Brain performed at Indiana University will have sequences including contrast, no contrast, FLAIR, DTI and PWI. If patient receives MRI Brain outside of Indiana University, a minimum of contrast, no contrast and FLAIR will need to be obtained and all sequences mentioned above are encouraged.
4. Variations of -30 days from the scheduled visit are permitted for linear accelerator based SRS, and may include the baseline screening MRI at the treating radiation oncologist's discretion.
5. Will be calculated using www.brainmetgpa.com tool
6. Diagnostic brain MRI is considered standard of care and will be performed as part of standard of care if subjects have not already undergone the procedure prior to enrollment.
7. Height is only required at the baseline screening visit.
8. After 12 months, only clinically relevant AEs will be recorded.

* Subjects may be treated multiple times. Subjects cannot be enrolled if the treatment will have a dose overlap within the target from prior treatments of 20% or greater. Once it is determined that they will receive treatment if they are in follow-up, they will be enrolled onto cohort 2 and re-start all procedures beginning with baseline screening.

TREATMENT DOSE AND DELIVERY

The total radiosurgery dose will be specified according to tumor size as noted in Table 1. All patients will be treated to this dose in one session.

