10.1 General Concomitant Medication and Supportive Care Guidelines

For patients presenting with signs and symptoms relatable to peri-tumoral edema, including but not limited to nausea and headaches, dexamethasone will be prescribed at a dose level per clinician judgement.

For patients presenting with seizure, anti-seizure medication will be prescribed at a dose level per clinician judgement. No specific type of anti-seizure medication is recommended or prohibited.

Each patient will be given a prescription for 1mg Ativan to be taken approximately 30 minutes prior to the procedure, or otherwise at the physician's discretion.

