12.2 Symptomatic Radiation Necrosis

Assessment for symptomatic radiation necrosis will be performed based on patients meeting criteria for radiographic radiation necrosis who require steroid administration, bevacizumab, and/or operative resection to treat symptomatic cerebral edema. These will be assessed at each post-SRS follow-up visit in conjunction with Brain MRIs.

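### The primary outcome measure (4.1) omits bevacizumab-treated symptomatic necrosis that the primary objective (3.1) and the assessment section (12.2) count, and nothing says which wording governs

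*Combined protocol and SAP*

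**What the plan says.** The primary event is worded four times in the combined protocol and SAP.

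- 3.1 Primary Objective: symptoms "requiring steroid administration (i.e. Decadron), bevacizumab (Avastin), and/or operative intervention", with matching imaging.
- 12.2 Symptomatic Radiation Necrosis: patients with radiographic necrosis who "require steroid administration, bevacizumab, and/or operative resection to treat symptomatic cerebral edema". It adds: "These will be assessed at each post-SRS follow-up visit in conjunction with Brain MRIs".
- 4.1 Primary Outcome Measure: symptoms "requiring steroid administration (i.e. Decadron) and/or operative intervention concomitant with advanced and routine brain imaging findings".
- Section 2, Summary and Rationale: "radionecrosis will be defined as clinical symptomatology following SRS requiring steroid utilization and/or operative intervention".

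The sample size section (14.4) and the primary analysis (14.7) speak only of symptomatic radiation necrosis and cite no definition. Section 8.6 refers to Section 12, but for reading the MRI.

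14.4 takes a historical rate of 16% and an expected rate of 5%, with 40 evaluable patients, and calls the dose reduction desirable if at most 4 have the event. 14.7 tests against 16% with a one-sided exact binomial test at 5%.

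On ICI, section 2 defines concurrent therapy as ICI given within 30 days of SRS and takes the 16% from the concurrent SRS + ICI literature. Inclusion criterion 9 (5.1) makes patients with ICI in the 30 days before SRS eligible. Section 8.4 leaves starting or continuing ICI to the medical oncologist. The populations in 14.3 are defined by radiation alone.

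**The concern.** 3.1 and 4.1 are otherwise almost identical sentences, so the missing drug changes who is counted. A symptomatic patient with necrosis on imaging who receives bevacizumab alone is an event under 3.1 and 12.2 and a non-event under 4.1 and section 2. The case is foreseeable: section 2 mentions bevacizumab as a treatment for symptoms and links steroid use to poorer survival on ICI.

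The conclusion rests on a handful of events, and the narrower wording can only lower the count. If the choice is left open, it could be made after the count is known.

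The ICI gap is of a different kind. A patient with no ICI within 30 days of SRS could enter a primary rate that is compared with a null drawn from concurrent treatment.

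**Working it through.** **Who is counted**

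| Section | Steroids | Surgery | Bevacizumab alone |
|---|---|---|---|
| 3.1 | yes | yes | yes |
| 12.2 | yes | yes | yes |
| 4.1 | yes | yes | no |
| 2 (rationale) | yes | yes | no |

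Every narrow event is also a broad event, so the narrow count never exceeds the broad count.

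**The plan's own figure.** Inputs from 14.4: null 16%, alternative 5%, type I error below 10%, power 80%. With success defined as X ≤ c and X ~ Bin(n, p), the smallest n meeting both conditions is 40, with c = 3: P(X ≤ 3 | 0.16) = 0.098 and P(X ≤ 3 | 0.05) = 0.862. So 40 reproduces. The written cut-off of 4 gives 0.211 and 0.952. The 5% test in 14.7 rejects at n = 40 only for c = 2 (0.035 and 0.677). That these cut-offs disagree is a separate matter. All three are carried below so that the result does not depend on which is kept.

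**Probability of opposite conclusions.** Let X be the broad count, p the true broad rate, and b the share of SRN cases treated with bevacizumab only. The documents give no value for b; 5% and 10% are assumed. Given X = x, the narrow count Y is Bin(x, 1 − b), so

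P(opposite) = Σ over x > c of P(X = x) · P(Y ≤ c | x).

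Because Y ≤ X, this equals P(Y ≤ c) − P(X ≤ c), with Y ~ Bin(40, p(1 − b)).

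Example, c = 4 and p = 0.16:
- b = 0.05: narrow rate 0.152; 0.2522 − 0.2110 = 0.041.
- b = 0.10: narrow rate 0.144; 0.2986 − 0.2110 = 0.088.

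| Cut-off | p = 16% (b = 5% / 10%) | p = 10% | p = 5% |
|---|---|---|---|
| ≤ 4 (14.4 as written) | 0.041 / 0.088 | 0.041 / 0.081 | 0.008 / 0.015 |
| ≤ 3 (meets 14.4's 10%) | 0.025 / 0.055 | 0.042 / 0.086 | 0.018 / 0.034 |
| ≤ 2 (14.7 test) | 0.011 / 0.025 | 0.032 / 0.067 | 0.028 / 0.055 |

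These figures do not depend on what the 16% counts. A share of 20% would give 0.196 at p = 16% and 0.027 at p = 5% under ≤ 4, but nothing in the documents points to a share that large.

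**When one patient decides.** Under ≤ 4, a single bevacizumab-only patient reverses the conclusion only if the broad count is exactly 5. P(X = 5) is 0.154 at 16%, 0.165 at 10% and 0.034 at 5%.

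**Cost of the broader event.** Suppose the 16% and 5% exclude bevacizumab-only cases. The broad rate under the alternative is then 0.05/(1 − b) = 0.0526 or 0.0556.

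| Cut-off | Power at 5% | b = 5% | b = 10% |
|---|---|---|---|
| ≤ 4 | 0.95 | 0.94 | 0.93 |
| ≤ 3 | 0.86 | 0.84 | 0.82 |
| ≤ 2 | 0.68 | 0.65 | 0.62 |

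Under the null the broad rate is 0.16/(1 − b) = 0.168 or 0.178, and P(X ≤ 4) falls from 0.211 to 0.173 or 0.138. The broader event is therefore conservative in that case.

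**The case against.** The strongest reply is that this is one missing word. The definitions are nested, 12.2 is the section that says how SRN is assessed, it agrees with the stated objective, and section 2 is background. Section 10.1 says that for symptoms of peri-tumoral edema "dexamethasone will be prescribed at a dose level per clinician judgement", so few patients should receive bevacizumab and no steroid. All of this stands, and it limits the size. It does not settle which wording governs, because 4.1 is the section that defines the primary outcome.

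Several stronger readings are tempting and are not supported:

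- **The definitions are incompatible.** They are nested and differ for one kind of patient.
- **One patient can always reverse the result.** That holds only at exactly 5 broad events.
- **The type I error is inflated from 0.21 to 0.25 or 0.30.** This needs the 16% to count bevacizumab-only cases, which the documents do not say. If it excludes them, 4.1 matches its null. The 0.21 itself belongs to the cut-off of 4, not to this issue.
- **Bevacizumab goes unrecorded at visits.** The history in 8.6 ("A detailed medical history (including necessity of any steroid administration") and the calendar ("Medical History (including steroid usage") name only steroids, but as an inclusion and not as a limit, and 12.2 has all three treatments assessed at each visit.
- **Broadening the event leaves power above 80% throughout.** Under the 14.7 test power is 0.68 before any change.
- **Criterion 9 contradicts the definition of concurrent ICI.** It is permissive and covers only ICI before SRS. The gap is that nothing requires ICI, while the intent to study patients on ICI is clear from sections 2 and 3.1.

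**Conclusion.** The inconsistency is real and sits in the operative text. Following 4.1 as written drops events that the primary objective counts, always in the direction of success. The likely effect is modest: with an assumed 5% or 10% bevacizumab-only share, the chance of opposite conclusions under at most 4 of 40 is 0.04 or 0.09 at a true rate of 16%, 0.04 or 0.08 at 10%, and 0.01 or 0.02 at 5%. Under the 14.7 test it is 0.01 or 0.02 at 16% and 0.03 or 0.06 at 5%. These figures rest on the assumed shares and on 40 independent evaluable patients.

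The ICI gap is separate and smaller. No size is attached to it, because the documents give neither the share of analysed patients without concurrent ICI nor their SRN rate at these doses.

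**What to change.** **Event definition.** Add bevacizumab to the event in 4.1 and in section 2 so that they match 3.1 and 12.2. State in 14.4 and 14.7 that this is the event counted. Report the count without bevacizumab-only cases as a sensitivity analysis. Do this before the primary count is reviewed. Naming bevacizumab beside steroids in 8.6 and the study calendar is optional, since 12.2 already covers it. The change concerns which events are counted, not how patients are treated.

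**ICI.** Reconcile section 2, criterion 9, 8.4 and 14.3. Report how many patients in the primary analysis actually received ICI within 30 days of SRS, and show the primary rate in that subset as a sensitivity analysis only. Restricting the primary set instead could take it below 40, because the total of 42 leaves room for two non-evaluable patients. It could also select patients on what happens after SRS.

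**Cost.** A few lines of wording and the Board approval that protocol changes need; the sample size stays as it is. If the 16% and 5% exclude bevacizumab-only cases, the test becomes slightly conservative, with a loss of power of 0.01 to 0.02 under ≤ 4, 0.02 to 0.04 under ≤ 3 and 0.03 to 0.06 under the 14.7 test. That last test is already below 80% for a separate reason.
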